## 7.6.6 Adverse Event Reporting

Investigators are responsible for monitoring the safety of subjects who are participating in this study and for alerting the sponsor of any event that seems unusual, even if this event may be considered an unanticipated benefit to the subject.

### 7.6.7 Serious Adverse Events Reporting

[REDACTED] will be responsible for the overall pharmacovigilance process for this study. All SAEs, related to the experimental treatment or not, occurring during the course of the study must be reported on an SAE form to [REDACTED] (see below) within 24 hours of the knowledge of the occurrence (this refers to any AE that meets one or more of the aforementioned serious criteria). The SAE reporting period ends at the end of the follow-up period or if the subject begins an alternative therapy.

Reporting should be done by sending the completed SAE form to the following e-mail address (faxing can also be done as a second option in case e-mailing is not possible).

Safety Contact Information: **PPD**

E-mail: **PPD**

Fax: **PPD**

[REDACTED] will inform the sponsor, primary medical monitor, and CRO within 1 business day of awareness of a new SAE. [REDACTED] will process and evaluate all SAEs as soon as the reports are received. For each SAE received, [REDACTED] will make a determination as to whether the criteria for expedited reporting to relevant regulatory authorities have been met. [REDACTED] will manage the AE reporting, including suspected unexpected serious adverse reactions, in accordance with the applicable local regulations. SAEs will be reported to the IRB/EC as per local IRB/EC requirements.

The study sponsor will be responsible for notifying the Food and Drug Administration (FDA) of any unexpected fatal or life-threatening suspected adverse reactions as soon as possible, but in no case later than 7 calendar days after the sponsor's initial receipt of the information. In addition, the sponsor must notify the FDA and all participating investigators in an Investigational New Drug (IND) safety report of potential serious risks, from clinical trials or any other source, as soon as possible, but in no case later than 15 calendar days after the sponsor determines that the information qualifies for reporting.

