 Brief physical examinations.

 Only at ET

 ECG will be recorded at 0 (pre-dose, within 1 hour of dosing), 1 (± 30 min), and 3 (± 1 hour) hours post-dose on Day 1 and Week 4. ECG will be recorded only once at screening, Week 12, and ET visits.

 If PPD is used, a second screening visit will be necessary.

 Optional, only for a subset of approximately 68 subjects who consent: two 4.5-mm skin biopsies at Day 1 (one from lesional skin and one from adjacent nonlesional skin) and one at Week 12/ET (from lesional skin). Subjects consenting to biopsies collection must also consent to PD samples. Biopsies should be collected prior to study product administration.

 Optional, only for a subset of approximately 68 subjects who consent: PD samples to be drawn as trough samples prior to study product administration. Subjects consenting to PD samples must also consent to biopsies collection. PD samples should be collected prior to study product administration.

 An additional skin biopsy from lesional skin and PD sample will be collected at Week 4 for subjects who consent to four biopsies.

 PK samples will be collected at 0 (pre-dose), 1 (± 30 min), 3 (± 30 min), and 6 (between 5 to 12 hours post-dose) hours post-dose. The dosing time for the previous day should be recorded accurately.

 PK samples will be collected at 0 (pre-dose) and 2 (± 30 min) hours post-dose. The dosing time for the previous day should be recorded accurately. At ET and Week 12, only one PK sample will be collected.

 Follow-up visit for subjects not participating in the OLE study. Subjects who have their study product discontinued due to the start of a prohibited medication for the treatment of AD or for any other safety reasons will be asked to come back for an additional follow-up visit about 4 weeks after the study product discontinuation (in addition to the ET visit). Refer to section 6.4.2 for more details.

 Study products will be taken at home daily for 12 weeks, except on study visit days when the study products will be administered on site. No drug administration will be given at Week 12 visit as part of the present study.

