#### **5.3.1 Discontinuation**

Subjects who discontinue the study after the first dose will be asked, if they agree, to come for a last assessment (ET visit). Subjects who receive an active treatment for AD after Week 4 visit are not necessarily discontinued from the study (refer to section [6.4.2](#) for more information on how to proceed with these subjects). Subjects who have their study product discontinued due to the start

of a prohibited medication for the treatment of AD or for any other safety reasons will be asked to come back for an additional follow-up visit about 4 weeks after the study product discontinuation (in addition to the ET visit).

Subjects who did not complete the study for reasons other than safety, or have demonstrated significant noncompliance to study treatments based on IP accountability (define as subject who received <80% or >120% of the scheduled doses during the study treatment period) will be evaluated by the principal investigator or designee at each visit and may potentially be replaced. If a subject drops out during the first 4-week period, the subject may be replaced at sponsor's discretion.

Reasons for discontinuation include the following:

- The investigator decides that the subject should be withdrawn. If this decision is made because of a serious adverse event (SAE), the study product is to be discontinued in that subject immediately and appropriate measures are to be taken. The investigator will notify the sponsor immediately.
- The attending physician requests that the subject be withdrawn from the study.
- The subject, for any reason, requires treatment with another therapeutic agent may be discontinued as detailed in section [6.4.2](#).
- The subject is lost to follow-up. In this case, a reasonable attempt to contact the subject and ascertain his or her status must be made, and these attempts must be documented.
- The subject becomes pregnant at any time during the study.
- The subject may withdraw from the study for any other reason, including withdrawal of consent.

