## 6.4.2 Prohibited Therapies or Procedures

**Table 3** lists prohibited medications that are not to be used from the defined washout periods before the first administration of study products at the Day 1 visit through the last study visit.

The discretionary use of concomitant treatments or therapies for atopic dermatitis is prohibited between Day 1 and Week 16 visit. However, should subjects experience an exacerbation of atopic dermatitis that requires, in the opinion of the investigator, the use of a prohibited therapy, the following approach should be followed:

1. The investigator needs to discuss the case with the medical monitor in order to obtain permission to use a prohibited medication.
2. Subjects who start prohibited medications as a treatment for AD within the first 4 weeks of the study will be discontinued from the study product (ASN002 or placebo) and will perform the ET visit at the time of discontinuation. In addition, the subject will be asked to come back for a follow-up visit 4 weeks after the study product is stopped. Collection of PD samples, PK samples, and skin biopsies will not be performed after the ET visit. These subjects will not be eligible to participate in the OLE study.
3. Subjects who start prohibited topical medications as a treatment for AD after the first 4 weeks of the study may continue all the study assessments up to the last study visit. Treatment with the study product may continue concurrently until the end of the treatment period, and these subjects will be eligible to participate in the OLE study afterwards. Collection of PD samples and skin biopsies will not be performed after the start of a topical medication.
4. Subjects who start prohibited oral corticosteroids as a treatment for AD after the first 4 weeks of the study will be discontinued from the study product (ASN002 or placebo). Use of oral corticosteroids after permanent cessation of ASN002 is permitted only for a short period of time (maximum 3 weeks). Subjects should come to all planned study visits for safety assessments up to the Week 12 visit. Collection of PD samples, PK samples, and skin biopsies will not be performed after study product discontinuation. These subjects will be eligible to participate in the OLE study if they meet the required washout period for prohibited medications as defined in the OLE study.

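### Protocol 7.6.7 ends 24-hour SAE reporting when a subject begins an undefined alternative therapy, although the plan keeps subjects who start other AD treatment under observation

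*Protocol*

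**What the plan says.** Protocol 7.6.7 states the general duty first: "All SAEs, related to the experimental treatment or not, occurring during the course of the study must be reported on an SAE form", within 24 hours of the site learning of the event. It then limits the period: "The SAE reporting period ends at the end of the follow-up period or if the subject begins an alternative therapy".

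Other sections describe what happens when a subject starts other AD treatment:

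- **5.3.1:** "Subjects who receive an active treatment for AD after Week 4 visit are not necessarily discontinued from the study".
- **6.4.2 item 3** (topical medication after the first 4 weeks): assessments may go on to the last visit, and "Treatment with the study product may continue concurrently until the end of the treatment period".
- **6.4.2 item 4** (oral corticosteroids after the first 4 weeks): study product stops, but "Subjects should come to all planned study visits for safety assessments up to the Week 12 visit".
- **6.4.2 items 2 and 5** (any prohibited AD medication in the first 4 weeks; other systemics later): study product stops, with an early termination visit and a further visit 4 weeks later. Section 5.3.1 and Table 1 footnote 12 repeat this: subjects "will be asked to come back for an additional follow-up visit about 4 weeks after the study product discontinuation".

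Two sections set the period for collecting and recording events. Section 7.6.1 collects AEs and SAEs from consent to the final visit or contact. Section 7.6.5 records them in the source document and eCRF to the end of participation. Neither makes an exception for subjects who start another therapy.

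**The concern.** The end of an expedited safety duty depends on a term that a site cannot look up. It appears only in this sentence. Where the protocol speaks of other treatment during the study, it uses different words: prohibited medication or therapy, active treatment for AD, another therapeutic agent. Two sites could apply the sentence differently to the same subject.

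The SAE form is at stake. Section 7.6.7 makes it the route by which a site reports an SAE to the pharmacovigilance group, which must then, for each SAE it receives, "make a determination as to whether the criteria for expedited reporting to relevant regulatory authorities have been met". A site that believed the period had closed could enter an SAE in the eCRF and send no form. The assessment for expedited reporting could then start late. Some of these subjects are being seen expressly for safety and, on one reading, some may still be taking study product.

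**Working it through.** The plan gives no figure to reproduce. The check sets the passages side by side under each possible meaning of the term, and then counts the days on which the 24-hour form would not be required.

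**Readings**

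- (i) Any other AD therapy, including a topical added to study product.
- (ii) Only therapy that replaces study product.
- (iii) Only therapy begun after the subject has left the study.

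**Inputs**

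- Nominal days from SAP 5.4: Week 4 = Day 28, Week 12 = Day 84, Week 16 = Day 112.
- Week 12 visit window: ±2 days (Table 1).
- Table 1 footnote 13: "No drug administration will be given at Week 12 visit as part of the present study". The last nominal dose is therefore on Day 84 − 1 = Day 83.
- Earliest start after the first 4 weeks: Day 29.

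**Topical added, study product continued (item 3).** Dosing days from a start on day s = 83 − s + 1.

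- s = 29: 83 − 29 + 1 = 55
- s = 43: 83 − 43 + 1 = 41
- s = 57: 83 − 57 + 1 = 27
- s = 71: 83 − 71 + 1 = 13

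With the Week 12 visit on Day 82 to Day 86, the last dose falls on Day 81 to Day 85. The Day 29 figure then runs from 81 − 29 + 1 = 53 to 85 − 29 + 1 = 57. A subject who does not enter the open-label extension (OLE) also has the off-drug interval from Week 12 to Week 16, 112 − 84 = 28 days.

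**Oral corticosteroid, study product stopped (item 4).** A start on Day 29 gives 84 − 29 + 1 = 56 days of off-drug observation to Week 12. With the visit window this is 82 − 29 + 1 = 54 to 86 − 29 + 1 = 58.

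**Items 2 and 5, study product stopped.** 4 × 7 = 28 days, approximately, to the follow-up visit, off drug.

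| Case | Reading (i) | Reading (ii) | Reading (iii) |
|---|---|---|---|
| Topical added (item 3) | up to about 55 dosing days | 0 | 0 |
| Oral corticosteroid (item 4) | up to about 56 days, off drug | up to about 56 days, off drug | 0 |
| Items 2 and 5 | about 28 days, off drug | about 28 days, off drug | 0 |

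These are possible durations for one subject. The documents give no rate of starting other AD therapy and no SAE rate, so the number of subjects or events affected cannot be derived.

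**The case against.** The strongest defence is that the two sentences of 7.6.7 are a general duty followed by its limit, and that nothing else contradicts the limit. Sections 5.3.1 and 6.4.2 and Table 1 govern visits, assessments and study product; none mentions an SAE form. This stands. A reader might infer a head-on conflict between 7.6.7 and those sections, but keeping a subject under observation does not logically exclude ending an expedited-form period. The fault is an undefined early end point that, read literally, can reach subjects the plan still follows for safety.

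The ordinary sense of the word also favours the sponsor. Alternative suggests instead of, and a topical used alongside study product is an addition. This stands too: the 55 dosing days belong to the broadest reading only, and reading (ii) involves no dosing days.

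There are other routes to the sponsor:

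- Section 6.4.2 item 1 requires the medical monitor's permission before a prohibited AD therapy is used, so these subjects should already be known to the monitor.
- Section 4.4 requires contact with the medical monitor at interruption or discontinuation.
- Section 5.3.1 requires immediate notice to the sponsor if the investigator withdraws a subject because of an SAE.
- Section 7.6.6 asks for an alert about any unusual event, and the DSMB reviews unblinded safety data.

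These reduce the exposure. None sets a 24-hour form for an SAE that occurs after the other therapy has begun.

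Two stronger inferences are tempting, and the documents do not support them:

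- **The regulatory clocks stop.** In 7.6.7 the 1-business-day notice runs from awareness of a new SAE, and the 7-day FDA limit from the sponsor's receipt of the information. Neither is tied to the form itself. A missing form can delay awareness, but it does not suspend either clock.
- **Safety data are lost, or SAE counts differ between arms.** That would need sites to stop capturing SAEs, contrary to 7.6.1 and 7.6.5. The rule in SAP 6.2 that sets data to missing after prohibited medication applies to efficacy data only. The serious-event summaries and listings in SAP 13.1 have no such cut.

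**Conclusion.** The point holds as a fault in a stated rule. Followed as written, 7.6.7 can end the 24-hour SAE form for subjects who remain under planned observation, and the reader cannot tell for which ones. On reading (ii) the lapse is confined to off-drug follow-up, up to about 56 days after an oral corticosteroid start and about 28 days under items 2 and 5. Up to about 55 nominal dosing days are added only if add-on topicals count. On reading (iii) there is no gap.

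The figures assume nominal visit days and the earliest possible start, Day 29, for the two longer periods. The exposure is limited to the timeliness of expedited reporting: no data, efficacy estimate or planned safety table is affected. It is still worth correcting, because an expedited safety duty should not depend on each site's reading of an undefined term and the correction is small.

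**What to change.** Replace the limiting sentence in 7.6.7 with one that removes the alternative-therapy cut-off and gives the SAE reporting period as in 7.6.1: from informed consent to the final visit or contact in this study. State that it applies to all subjects, including those who start AD medication under 6.4.2 and those who enter the OLE.

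Deleting the clause alone would not be enough. The remaining text would still end the period with follow-up, and subjects who enter the OLE have no follow-up period in this study.

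Check the Germany-only protocol Version 2.2, cited in SAP section 1 but not available here, for the same clause. No SAP change is needed, and no treatment, rescue or stopping rule is touched.

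The cost is a short amendment, which under the Statement of Compliance needs IRB/EC approval before it takes effect, across about 50 centers in three countries. A few more SAE forms may follow; their number cannot be derived from the documents.

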## 7.6.8 Pregnancy Reporting

If a female subject or a female partner of a male subject becomes pregnant during the study, the subject should inform the study site as soon as possible. Upon confirmation of the pregnancy, the female subject will be discontinued from the study. The investigator must complete a study-specific pregnancy form upon confirmation of a pregnancy and send it to [REDACTED] within 24 hours of confirmation of the pregnancy (contact information to be used is the same as for SAE reporting). [REDACTED] will report all cases of pregnancy to the sponsor and CRO in a timely manner. Posttreatment follow-up should be done to ensure subject safety. Pregnancy is not itself an AE or SAE; however, maternal/fetal complications or abnormalities will be recorded as AEs or SAEs, as appropriate. The investigator will follow the pregnancy until completion or until pregnancy termination and, in the case of a live-born offspring, to 1 month of age in that infant. The investigator will notify [REDACTED] and CRO of the outcome as a follow-up to the initial pregnancy form. All pregnancies should be reported to the sponsor and, when applicable, to the ethics committee.

In the case of an SAE or pregnancy, the subject treatment assignment may be unblinded if judged necessary by the investigator and/or medical monitor in consultation with the sponsor. Once the subject treatment assignment is unblinded, the subject for whom the blind has been broken will be discontinued from the study and undergo the ET procedures.

## 7.6.9 Overdose

Study drug overdose is any accidental or intentional use of study drug in an amount higher than the dose indicated per protocol for a given subject. Study drug compliance (see section 6.3.2) should be reviewed to detect potential instances of overdose (intentional or accidental).

Any study drug overdose during the study should be recorded on the source document and eCRF. In the event of overdose, the subject should be closely monitored for any potential AEs. All AEs associated with an overdose should be entered on the Adverse Event eCRF and reported using the procedures detailed in section 7.6.7, Serious Adverse Events Reporting, even if the events do not meet seriousness criteria. If the AE associated with an overdose does not meet seriousness criteria, it must still be reported using the SAEs reporting procedures and in an expedited manner, but should be noted as non-serious on the form and the Adverse Event eCRF. The excess quantity and duration of the overdose should be recorded.

## 8 STATISTICAL CONSIDERATIONS

### 8.1 Sample Size Determination

Using the following assumptions for the primary efficacy endpoint: a change-from-baseline in EASI at week 12 of at least -15 in the ASN002 dosing groups, a change-from-baseline of -8 in the placebo group, a common standard-deviation of 8, nominal alpha of 0.0167 for each comparison of interest, we would need 40 evaluable subjects per group in order to achieve a power of 92% on the primary efficacy endpoint.

Moreover, with 46 subjects per group, we would have 80% power to show a statistically significant difference between the higher dosing group and placebo in IGA responses (one of the key secondary efficacy endpoint), assuming a response of 37.5% vs. 11.1% in the higher dosing and placebo groups, respectively, using an alpha of 5%.

Thus, assuming about 15% dropout rate, 55 subjects per group will need to be enrolled in this trial for a total of 220 subjects in order to have a minimum of 46 subjects per group to evaluate efficacy with adequate power.

### 8.2 Populations for Analyses

Modified Intent-to-Treat Population (mITT): This population will include all subjects who received at least one dose of the study product. All subjects will be analyzed according to the treatment group to which they were randomized. The mITT population will be used as the primary analysis population for efficacy.

The Per Protocol Population (PP): This population will include all subjects who were randomized, who received at least one dose of study product, with no significant protocol deviations, and who provided evaluable data for the primary endpoint. All subjects will be analyzed according to the treatment group that they actually received.

The Safety Population (SAF): This population will include all subjects who received at least one dose of the study product. All subjects will be analyzed according to the treatment group that they actually received.

The PK Population: This population will include all subjects who received at least one dose of ASN002 and have plasma concentration data.

The PD Population: This population will include all subjects who have at least one assessments of PD parameters

## 8.3 Statistical Analyses

### 8.3.1 General Approach

Continuous variables will be summarized in tables and will include the number of subjects, mean, standard deviation, median, minimum, and maximum. Categorical variables will be presented in tables as frequencies and percentages.

The primary efficacy analysis will be done using the mITT population and the PP population will be used as supportive analysis. All efficacy analyses will be performed using Mixed Model Repeated Measures (MMRM) analyses as primary analyses to take care of missing observations. Moreover, the analyses performed on observed case (i.e. without imputation of missing observations) will be done as sensitivity analyses.

Additional details regarding the efficacy and safety variable definitions, analyses strategy, control of the overall type 1 error, statistical justification, and techniques for handling missing values (e.g. for subjects who started prohibited medications) will be detailed in a SAP that will be prepared before the database is locked and any analyses are undertaken.

### 8.3.2 Efficacy Analyses

The primary efficacy endpoint will be analyzed using a repeated measures analysis of covariance on change-from-baseline variable to compare the time profile between treatments where the visit will be the time factor; and the stratification factors, treatment group, and interaction term for treatment-by-visit will be the fixed effects and the baseline value will be the covariate. An unstructured variance-covariance matrix will be used. Additional interaction terms will also be included in supportive statistical models and will be detailed in the SAP.

